4.5 Sample Size Determination

Sample size for the study was based on the number of treated subjects in LAL-CL01 who were eligible and willing to participate in this extension study.

5. STATISTICAL ANALYSIS

5.1 General Statistical Methodology

All data will be provided in listings sorted by cohort and subject study number, and, if applicable, date of assessment. Dates will be provided in the ISO8601 yyyy-mm-dd format (eg, 2013-01-01). Where a time component is included (24 hour clock with hour and minute) the format will be yyyy-mm-dd:hh:mm (eg, 2012-01-01:16:32). Included in all listings will be the dosing cohort for each subject. Select listings will also include the dosing regimen that each subject was on at the onset of the event.

Tabulations will be prepared using the following descriptive statistics:

- Continuous, quantitative variable summaries will include the number of subjects with non-missing values (n), mean, standard deviation (SD), minimum, median, and maximum. In addition, the percent coefficient of variation (CV%) will be provided for PK parameters.
- Categorical, qualitative variable summaries will include the frequency and percentage of subjects who are in the particular category. In general, the denominator for the percentage calculation will be based upon the total number of subjects in the analysis set for the cohort. Shift tables comparing data observed at baseline to that observed after the initiation of dosing will be prepared as noted for specific endpoints.

95% two-sided confidence intervals (CI) may be calculated around the estimates based on the exact binomial distribution for categorical endpoints and the t-distribution for continuous endpoints. Confidence intervals will be based on a 2-sided alpha of 0.05 and are intended to guide clinical judgment and interpretation of the data. Effect of anti-drug antibodies may be examined for efficacy, safety, and PK endpoints. Additional exploratory analyses may be conducted in other subgroups of interest.

Baseline values are defined as the last measurement prior to the first infusion of SBC-102 in study LAL-CL04.

For select continuous efficacy, safety, and HRQOL endpoints that are computed as changes from baseline, change from the CL04 Baseline will be presented. All tabulations will present data overall and by dosing cohort.

Subjects who miss infusions do not "make up" those infusions, rather, they continue with the procedures stated in the protocol as if they had not missed the infusions. If a subject misses more than 3 consecutive planned infusions, laboratory data for that subject will not be included in summaries, beginning with the first of the multiple missed doses. Adverse event summaries will, however, include any events reported for such a subject.

P-values and confidence intervals are considered descriptive and are not adjusted for multiplicity.

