2.2.4 Pharmacodynamic Endpoints

The PD endpoints include observed values, change from baseline and percent change from baseline for hepatic transaminases, serum lipids and acute phase reactants at each time of assessment, overall and by dosing cohort. The percentage of subjects with abnormal transaminases at each time point will also be summarized overall and by dosing cohort.

Exploratory disease-related biomarkers, which may be identified, based on emerging information from the SBC-102 development program and scientific literature will be analyzed by changes or percent changes from baseline if the assessments are continuous.

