5.3 Handling of Missing Data

All data will be analyzed as they were collected in the database. Missing data generally will not be imputed using statistical or manual methods.

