9. PHARMACODYNAMIC ANALYSIS

Analysis of pharmacodynamic endpoints will include summaries of liver biochemical parameters (ALT, AST, GGT, total bilirubin, bilirubin, albumin, and alkaline phosphatase), serum lipids (serum total cholesterol, LDL, HDL, and triglycerides), serum ferritin, hsCRP, and platelets which will be tabulated overall and by dosing cohort. Observed values, change from baseline and percent change from baseline at each time of assessment will be summarized, and will include 95% confidence intervals. P-values may be calculated if there are a minimum of 6 subjects across all cohorts available for analysis at a particular timepoint; if presented, these will be computed using Wilcoxon-sign-rank statistics on change from baseline.

Serum lipids, serum ferritin, and hsCRP will be presented by-subject and tabulated in both SI and Conventional units; all other laboratory data will be presented as SI units only. In addition, the proportion of subjects with abnormal transaminases, serum lipids, serum ferritin and hsCRP will be displayed by cohort and overall.

Shift tables comparing the percentages of subjects (pooled across dosing cohorts) with normal/abnormal values for each pharmacodynamic parameter at each time of assessment relative to the CL04 baseline will be presented.

Graphical displays may be created to illustrate the time course of these lab parameters, including spaghetti plots and mean plots. Graphical displays may also be used to investigate differences in lipid results from assessments taken one week after infusion versus those taken 2 weeks after infusion.

Change from baseline analyses for PD endpoints will be performed using CL01 and CL04 baselines.

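### By-visit percentages default to the whole analysis set as denominator, so unassessed subjects pull down both the abnormal and the normal percentage

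*SAP*

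**What the plan says.** SAP 5.1 gives the rule for categorical variables, qualified as holding in general: "the denominator for the percentage calculation will be based upon the total number of subjects in the analysis set for the cohort". The qualifier makes it a default. The bullet before it, for continuous variables, reports the count of subjects with non-missing values.

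Several by-visit summaries fall under the categorical default:

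- SAP 2.2.4: "The percentage of subjects with abnormal transaminases at each time point will also be summarized overall and by dosing cohort".
- SAP 9: "the proportion of subjects with abnormal transaminases, serum lipids, serum ferritin and hsCRP will be displayed by cohort and overall".
- SAP 9 again: "Shift tables comparing the percentages of subjects (pooled across dosing cohorts) with normal/abnormal values for each pharmacodynamic parameter at each time of assessment".
- SAP 11.3 (laboratory shift tables) and SAP 11.5 (ECG categories).

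None of these sections gives another denominator or asks for a missing category.

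Other provisions determine who can be absent at a visit:

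- Under SAP 5.2, one complete infusion and one post-treatment measurement put a subject in the Full Analysis Set, whatever happens later.
- Protocol 4.7 does not replace subjects who discontinue.
- SAP 5.3 states: "Missing data generally will not be imputed using statistical or manual methods".
- After more than 3 consecutive missed infusions, SAP 5.1 says "laboratory data for that subject will not be included in summaries, beginning with the first of the multiple missed doses".

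**The concern.** At the same visit, mean ALT would rest on the subjects measured and the percentage with abnormal ALT on everyone in the analysis set. The two figures would describe different groups, and nothing in the specified categorical table would show it.

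The SAP expects some thin visits. Section 9 allows p-values only when at least 6 subjects are available at a timepoint; with 9 enrolled, falling below 6 means 4 or more are absent. Follow-up is also long: up to 5 years in Protocol 3.2.3, although SAP 3.1 says up to 3.

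The study plans no formal hypothesis tests, so these descriptive tables are its results, and SAP 4.1 says summaries of available data may support regulatory filings. A percentage abnormal that drops because subjects were not measured could be read as a treatment effect.

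**Working it through.** The documents give no abnormality rate or dropout rate, so there is no stated figure to reproduce. The check applies the rule as written.

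**Inputs**
- N = 9, the maximum in Protocol 4.2. Full enrolment is an assumption.
- m = analysis-set subjects without a result at the visit. The documents give no value; 0 to 4 is assumed.
- x abnormal and y normal among those assessed, with x + y = N − m.
- Exact binomial 95% two-sided intervals, the method in SAP 5.1.

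**Step 1: the two denominators.** The SAP default gives x/N and y/N, which sum to (N − m)/N. The assessed denominator gives x/(N − m) and y/(N − m), which sum to 1. The default figure is (N − m)/N times the assessed figure, so it is lower whenever m > 0 and the count is not zero. This holds for the normal percentage as well as the abnormal one.

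**Step 2: loss unrelated to status.** With a constant true rate p, the expected reported rate is p × (N − m)/N.

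| m | True 66.7%, reported as | True 90%, reported as |
|---|---|---|
| 0 | 66.7% | 90% |
| 1 | 59.3% | 80% |
| 2 | 51.9% | 70% |
| 3 | 44.4% | 60% |
| 4 | 37.0% | 50% |

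For m = 3: 66.7% × 6/9 = 44.4%.

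**Step 3: selective loss.** Suppose 6 of 9 are abnormal at baseline and nobody's status changes.

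| Lost | % abnormal, SAP default (95% CI) | % abnormal, assessed (95% CI) |
|---|---|---|
| None | 6/9 = 66.7% (29.9–92.5) | 6/9 = 66.7% (29.9–92.5) |
| 2 abnormal | 4/9 = 44.4% (13.7–78.8) | 4/7 = 57.1% (18.4–90.1) |
| 3 abnormal | 3/9 = 33.3% (7.5–70.1) | 3/6 = 50.0% (11.8–88.2) |
| 2 normal | 6/9 = 66.7% (29.9–92.5) | 6/7 = 85.7% |

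When 2 normal subjects are lost, the percentage normal is 1/9 = 11.1% under the default and 1/7 = 14.3% among those assessed. The default's two percentages then sum to 66.7 + 11.1 = 77.8%, which is 7/9.

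**Step 4: within a cohort.** In an assumed cohort of 3, all abnormal, one unassessed subject turns 2/2 = 100% into 2/3 = 66.7%.

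**The case against.** **The rule is only a default.** This is true, and a programmer could choose otherwise. SAP 5.1 also does not say whether a subject whose laboratory data are withheld after missed infusions leaves the denominator. But no exception is named, so following the text gives N, and choosing a denominator once the data are in is a data-dependent decision.

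**Consequences are limited.** The primary objective is safety, and for incidence of adverse events the analysis-set denominator is appropriate. Intervals for proportions are optional in SAP 5.1. With at most 9 subjects, the listings, the non-missing n for the same continuous analytes and the per-subject plots in SAP 11.3 let a careful reader find the gaps. This stands, and it limits the severity, but the tabulated percentages would still be off.

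**The assessed denominator is not unbiased.** This also stands. In Step 3, losing 2 abnormal subjects moves the assessed rate from 66.7% to 57.1% although nobody improved. Under informative dropout neither denominator recovers the true rate.

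**An assessed-only rule can err the other way.** Coagulation tests are repeated only after an abnormal result (Protocol 5.1.10 and Appendix A). Extra liver and lipid panels follow dose or lipid-therapy changes (Protocol 5.1.10), and lipids may be monitored more often after abnormal results (Appendix A). Among subjects tested for such reasons, abnormality would be overstated. The fix must allow for this.

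**Stronger readings that the documents do not support.**
- A reader might infer that missing subjects are counted as normal. SAP 5.1 counts subjects who are in a category; a missing subject is in neither, so the percentage normal is pushed down too.
- A reader might infer that the bias always favours the drug. It does so for percentages abnormal and works against the drug for percentages normal.
- A reader might infer that the reported abnormal rate must drift down as follow-up thins. With nobody's status changing, it falls only if abnormal subjects are lost. If only normal subjects are lost it stays at 6/9, while still understating the rate among those assessed.

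**Conclusion.** The point holds as a defect in a stated default. Followed as written, SAP 5.1 puts every by-visit percentage with a non-zero count below its value among those assessed, by the factor (N − m)/N, whenever anyone is unassessed. At N = 9, each unassessed subject takes one ninth off the expected figure; with 3 unassessed, 66.7% becomes 44.4%. Any exact interval would treat unassessed subjects as observed.

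The size depends entirely on missingness, which the documents do not give. The values of m, the baseline of 6/9 and the cohort of 3 are assumptions. With complete data the error is zero.

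Severity is should-fix: the results are descriptive, the primary safety incidences are unaffected, and the correction is cheap.

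**What to change.** Add to SAP 5.1, in substance:

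- For by-visit categorical summaries and shift tables, the denominator is the number of subjects with a non-missing result at that scheduled visit, and also at baseline for shift tables.
- Each such table shows n/N and a missing row, and any exact interval uses that n.
- Analysis-set N is kept for whole-study incidence: AEs, SAEs, IARs, concomitant medication and disposition.
- Conditionally repeated coagulation tests and unscheduled or extra panels are left out of the assessed-only by-visit percentages, or reported separately with the reason for testing.
- State whether a subject whose laboratory data are withheld after more than 3 consecutive missed infusions appears in the missing row.

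The cost is a short SAP paragraph and a change to the table programming default; no new data are needed. Intervals at thin visits become wider: in the example with 2 abnormal subjects lost, the width goes from 78.8 − 13.7 = 65.1 to 90.1 − 18.4 = 71.7 percentage points. The assessed-only rate can still mislead if dropout is informative; n/N and the missing row make that visible but do not remove it.

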7.1.2 Laboratory Test Abnormality

Laboratory test results will be recorded, or provided on the laboratory reports submitted directly from the central laboratory. Out of range laboratory test values should not be reported as AEs UNLESS they are considered to be a clinically significant abnormality by the Investigator.

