Appendix E: Dose Modification and Stopping Rules for Study LAL-CL04

In the absence of an approved grading scale that can be applied to specific patient populations, this protocol will apply the National Cancer Institute Common Toxicity Classification of Adverse Events (NCI CTCAE), version 4.0 or higher. (http://evs.nci.nih.gov/ftp1/CTCAE/CTCAE_4.03_2010-06-14_QuickReference_8.5x11.pdf).

The following dose modification and stopping rules apply to the decision to pause dosing in individual subjects:

For IARs (refer to the definition in Section 7.1.3), the following stopping rules will apply:

• Subjects who develop a Grade 3 (severe) or higher IAR, defined as significant hypo/hypertension, increased temperature and rigors, significant tachypnea with wheezing and/or stridor, **OR** are IgE or skin test positive must stop treatment until their information is reviewed by the SC. Dosing with alterations to the dose or infusion regimen (e.g., pretreatment and/or slowing the rate of infusion) may resume once the SC and the Sponsor approve. Confirmation may also be sought from regulatory authorities prior to resuming dosing. Subjects with Grade 1 (mild) and/or Grade 2 (moderate) IARs can continue in the study. The SC and/or Sponsor may recommend alterations to the infusion regimen (e.g., pretreatment (e.g., pretreatment and/or slowing the rate of infusion).

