2.2 Study Endpoints

2.2.1 Safety Endpoints

This study is designed primarily to evaluate the safety and tolerability of long-term treatment with SBC-102, administered as weekly (qw) and biweekly (qow) IV infusions. The primary safety endpoints in this study will include:

- The incidence of:
 - Adverse events (AEs).
 - Serious adverse events (SAEs).
 - Infusion Associated reactions (IARs).
- Change/shift from baseline in:
 - Vital signs.
 - Physical examination findings.
 - Clinical laboratory tests.
 - 12-lead ECG parameters.
 - Use of concomitant medications/therapies.
- Characterization of anti-drug antibodies (ADAs) including:
 - Antibody positive rate.
 - Time to first antibody positive result.
 - Median and peak ADA titer.
 - Time to peak ADA titer.

A further characterization of ADAs, including neutralizing ADAs, may be performed as a separate pooled analysis across studies, and will be reported separately.

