11.3 Clinical Laboratory Evaluations

Observed measurements and changes/percent changes from the CL01 and CL04 baseline to study time points in clinical chemistry, hematology, and urinalysis will be summarized by dosing cohort and overall. All laboratory values will be classified as normal, above normal, or below normal based on normal ranges provided by the laboratory. All laboratory values will be presented in data listings. Results will be flagged to indicate if they were abnormal (high, low) and/or clinically significant. Frequencies of abnormal values relative to the laboratory normal range will also be summarized via shift tables.

Information relating to development of anti-drug antibodies will be provided in listings.

Spaghetti plots for actual, change from baseline, and percent change from baseline will be created for the following parameters: ALT, AST, GGT, total bilirubin, albumin, alkaline phosphatase, total cholesterol, LDL-C, HDL-C, triglycerides, hemoglobin, platelets, PT, PTT, and serum ferritin. Plots will include a line for each subject with line color to indicate cohort plus a black line for the overall mean.

Plots of mean absolute change and mean percent change over time with standard deviations as error bars may be prepared for the following:

- Liver biochemical parameters: ALT/AST, GGT, bilirubin, albumin, alkaline phosphatase
- Lipids: total cholesterol, LDL, HDL, triglycerides
- Other: Hemoglobin, platelets, PT/PTT, serum ferritin

Change from baseline analyses will be performed using CL01 and CL04 baselines.

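### The SAP's missed-infusion rule removes a subject's laboratory data from summaries with a start but no end and no reason; read literally, a subject who resumes dosing never re-enters the safety-laboratory or PD summaries

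*SAP*

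**What the plan says.** SAP 5.1 (General Statistical Methodology) deals with missed infusions in one short paragraph. Missed infusions are not replaced; instead the subjects carry on, and "they continue with the procedures stated in the protocol as if they had not missed the infusions". The trigger for the exclusion is more than 3 missed in a row, that is, four or more. From that point "laboratory data for that subject will not be included in summaries, beginning with the first of the multiple missed doses". The paragraph then makes one exception: "Adverse event summaries will, however, include any events reported for such a subject". It gives neither a point at which the exclusion stops nor a reason for it.

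The summaries that this touches are central to the study:

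- SAP 2.2.1 lists clinical laboratory tests under "Change/shift from baseline in" among the primary safety endpoints.
- SAP 11.3 plans changes from baseline for the safety laboratory data and adds "Frequencies of abnormal values relative to the laboratory normal range will also be summarized via shift tables".
- SAP 9 covers transaminases, lipids, ferritin and hsCRP: "Observed values, change from baseline and percent change from baseline at each time of assessment will be summarized".

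Protocol Appendix E provides for treatment to be paused after certain infusion reactions and says that dosing "may resume once the SC and the Sponsor approve". Protocol Section 8 allows part of a subject's data to be left out of the analysis, but requires the rationale to be set out in advance.

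**The concern.** A rule meant to keep untreated intervals out of the tables would need an end as well as a start. This one has only a start. A programmer who follows it as written drops every later laboratory value for that subject, including those taken after regular dosing has restarted. Another programmer might assume that the exclusion ends at resumption and would produce different tables from the same data.

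The primary objective is long-term safety, and the study enrols at most 9 subjects. One subject's missing years would therefore show in by-visit means, changes from baseline, shift tables and proportions abnormal. Adverse event tables only partly make up for this, because under Protocol 7.1.2 out-of-range values "should not be reported as AEs UNLESS they are considered to be a clinically significant abnormality by the Investigator". Values out of range but not judged clinically significant would drop out of the tabulations and remain in individual-level displays.

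**Working it through.** The plan gives no figure to reproduce, so the check has two parts: whether any other text closes the rule, and how many scheduled visits it removes.

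**Text.** No other section of the SAP or protocol gives an end or a reason. Protocol 8.7.2, which specifies the laboratory summaries, says nothing about dosing gaps. SAP 5.1 itself expects procedures to continue, and Appendix E expects that dosing may restart. Laboratory samples after a gap are therefore foreseeable.

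**Inputs (Protocol Appendix A).** Post-baseline scheduled visits, leaving out the Week 1 pre-dose draw and the extra draws after dose or lipid-drug changes:

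- Clinical laboratory tests: Weeks 4, 12, 24, 38, 52 (5 visits), then Weeks 66, 78, 90, 104 and the same pattern each year. Over 5 years, 5 + 4 × 4 = 21.
- Liver and lipid panels: Weeks 4, 8, 12, 16, 20, 24, 25, 32, 38, 52 (10 visits), then the same yearly pattern. Over 5 years, 10 + 4 × 4 = 26.

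**Assumed gap.** Four every-other-week infusions are missed, the first at week s, and dosing resumes at week s + 8. This is the shortest every-other-week gap that meets the trigger.

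**Formulas.** Removed = visits at week s or later. In gap = visits from s to s + 8 inclusive, because the resumption-day sample is pre-dose. After resumption = removed − in gap.

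| First missed dose | Clinical laboratory removed (of 21) | In gap | Liver/lipid removed (of 26) | In gap |
|---|---|---|---|---|
| Week 26 | 18 (86%) | 0 | 19 (73%) | 1 (Week 32) |
| Week 54 | 16 (76%) | 0 | 16 (62%) | 0 |
| Week 106 | 12 (57%) | 0 | 12 (46%) | 0 |

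The visits lost after resumption are thus 18, 16 or 12 for either panel.

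**Shorter study.** SAP 3.1 describes treatment for up to 3 years, where the protocol has 5. On 3 years the totals are 13 and 18 visits. The same gaps remove 10, 8 or 4 clinical laboratory visits and 11, 8 or 4 liver/lipid visits.

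**Longer gaps.** The number removed depends only on s, but the split changes with gap length. For s = 54 over 5 years, 16 visits of each panel are removed whatever the gap:

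- 8-week gap: 0 in gap, 16 after resumption.
- 26-week gap: 2 in gap (Weeks 66 and 78), 14 after.
- 52-week gap: 4 in gap (Weeks 66, 78, 90 and 104), 12 after.

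Now average the 3-year liver/lipid schedule over all start weeks from Week 6 with equal weight, which is an assumption. The share after resumption is then about 85% for an 8-week gap, 66% for 26 weeks and 47% for 52 weeks. If dosing never resumes it is zero.

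**Effect on precision.** With the SD held fixed, the 95% t-interval half-width is t(0.975, n − 1)/√n in SD units. For n = 9 this is 2.306/3 = 0.769. For n = 8 it is 2.365/2.828 = 0.836. Losing one of nine subjects widens the interval by about 9% (0.836/0.769 = 1.087).

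**The case against.** The strongest reply is that SAP 5.1 never says outright that post-resumption values are excluded. That is true. What is established is a missing end point, and the exclusion of later values follows from reading the rule literally.

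Several stronger readings are tempting, and the documents do not support them:

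- **That the rule mostly discards on-treatment data.** This holds for a subject who resumes after a short gap. It weakens as the gap lengthens and fails for a subject who stops infusions but keeps attending; there the rule removes only off-treatment values.
- **That the dropped values would be visible only in listings.** SAP 11.3 also plans plots with one line per subject for the main liver, lipid and blood-count parameters. The rule restricts summaries, and whether that covers these plots is not stated, so they may still show the values. Listings also flag high, low and clinically significant results.
- **That the safety results would be biased in a given direction.** Nothing in the documents shows how many subjects would meet the trigger or which way any bias would run.
- **That the rule is an undeclared departure from the protocol.** The protocol leaves analysis details to the SAP and is silent on dosing gaps. The rule's absence from SAP Section 14 is at most a documentation matter.

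It is also fair that all analyses are descriptive, that clinically significant laboratory abnormalities still enter the adverse event tables, and that leaving off-treatment values out of PD summaries is a defensible choice. None of this supplies the missing end point or the rationale that Protocol Section 8 asks for.

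**Conclusion.** The point stands as a should-fix. SAP 5.1 starts an exclusion and does not end it. Followed as written, it takes a subject who resumes dosing out of a primary safety endpoint's summaries and out of the PD summaries for the rest of the study.

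The counts in the table rest on a gap of exactly four every-other-week infusions, the Appendix A schedule, a 5-year course and a subject who resumes. They describe what happens to one such subject and do not predict how often it will happen. The actual effect on the study could be nil.

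**What to change.** Amend SAP 5.1 in two places.

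1. **Safety laboratory summaries.** Include all collected values for the Safety Analysis Set, with no exclusion based on dosing gaps.
2. **PD summaries.** If the exclusion is kept, limit it to samples from the first missed dose through the pre-dose sample on the day dosing resumes. Include all later samples, and state the reason for the exclusion, as Protocol Section 8 requires.

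The cost is a few sentences and the matching programming, with no protocol amendment and no new data.

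There are two downsides. Safety summaries will contain a few off-treatment values; for a four-infusion every-other-week gap that is at most 1 clinical laboratory visit, and at most 3 visits for any liver or lipid result shown there (for example Weeks 16, 20 and 24 for a gap from Week 16). PD summaries will contain values taken soon after dosing resumes, when the response may not yet have re-established. Because liver and lipid parameters appear under both SAP 9 and SAP 11.3, a footnote should explain any difference in n between the two sets of displays.
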